## 6. TREATMENTS AND MEDICATIONS

### 6.1. Prior Non-Radiation Anticancer Therapy

All prior non-radiation anticancer agents will be summarized categorically by Anatomical Therapeutic Chemical (ATC) Class Text and World Health Organization Drug Dictionary

(WHO-DD) substance preferred name by study treatment arm, type of therapy (systemic, local, unknown) and context of therapy (adjuvant, neoadjuvant, other) for ITT and PITT populations.

The following will be summarized categorically or with descriptive statistics as appropriate for all subjects in the ITT and PITT populations:

- Therapy type: Systemic (Neoadjuvant, Adjuvant, Other), Local, Unknown
- Number of prior local non-radiation anticancer agents for RCC per subject (1, 2,  $\geq 3$ ) and descriptive statistics
- Radiographic or clinical progression after initiation of the most recent agent (Yes, No)
- The time from the end of most-recent local non-radiation anticancer agent for RCC to randomization
- The time from the end of most-recent systemic adjuvant non-radiation anticancer agent for RCC to randomization

## **6.2. Prior Radiation Therapy, Surgery and Procedures**

Data obtained from the history of radiation therapy CRF will be summarized categorically or with descriptive statistics as appropriate for all subjects in the PITT and ITT populations:

- Subject incidence of radiation therapy by indication (RCC and Other)
- Number of prior radiation therapies for RCC per subject (1, 2,  $\geq 3$ ) and descriptive statistics
- Subject incidence of type of radiation therapy received for RCC or other indications
- Subject incidence of radiation therapy by site (Bone, Soft-tissue, Systemic, Unknown) for RCC or other indications
- Number and percent of subjects that received radiation by anatomic sites
- Number of subjects with prior surgery/procedure (Yes, No)
- Subject incidence of surgery type (Partial nephrectomy, Simple nephrectomy, Radical nephrectomy, Other)
- Time from the date of most recent surgery for RCC to randomization in months

## **6.3. Prior and Concomitant Medications (Excluding Anticancer Therapy)**

Prior and concomitant medications, other than prior and subsequent anticancer therapies, will be summarized by treatment group in the ITT and Safety populations by ATC and WHO-DD substance preferred name. Anticancer therapies are addressed in [Section 6.9](#) of this plan.

## **6.4. Prior and Concomitant Immune Modulating Medications**

Immune-modulating medications (IMMs) are a select list of medications that were used to manage AEs due to study treatment. A list of the verbatim terms for these medications will be identified and provided along with the ATC and WHO-DD base substance preferred name. These will be summarized by treatment group in the Safety population by ATC and WHO-DD base substance preferred name. In addition, the following summaries will be provided:

- Subjects with prior use of IMMs
- Subjects with concomitant use of IMMs
- Subjects with concomitant use of IMMs for management of AEs
- Subjects with concomitant use of high dose corticosteroids for management of AEs where high dose is defined as  $\geq 40$  mg/day of prednisone or equivalent

## **6.5. Study Treatment Exposure**

Study treatment exposure will be summarized descriptively and will include subjects in the Safety and P-Safety populations. Exposure summaries for the oral components and the infusion components will be presented separately.

The algorithms for calculating the various exposure parameters are described in [Table 4](#) for overall dosing summaries, [Table 5](#) for weight-based dosing summaries in cycle 1 – 4, and

[Table 6](#) for dosing summaries based on a flat dose from cycle 5 onwards.

**Table 4: Study Therapy Definitions (Overall summary)**

	Nivolumab	Ipilimumab	Cabozantinib/Placebo
Cumulative dose (mg)	Sum of doses administered to a subject	Sum of doses administered to a subject	Sum of doses administered to a subject
Number of infusions	Sum of all infusions administered	Sum of all infusions administered	N/A
Average daily dose (mg/day)	NA	NA	Cumulative dose (mg) / (Duration of exposure in days)
Relative dose intensity (%)	(Relative dose intensity (%) during weight-based infusions × number of weight-based infusions received + Relative dose intensity (%) of flat dose infusions × number of flat dose infusions received) / total infusions received	Sum of all relative cycle intensities / N	100 × average daily dose / (40mg/day)
Duration of exposure in days (including holds)	Last non-zero dose date of agent – first dose date of the agent +1	Last non-zero dose date of agent - first dose date of agent +1	Date of decision to discontinue or cut-off date – first dose date of agent +1
Duration of exposure in days (excluding dose holds)	Last non-zero dose date of agent – first dose date of the agent -total days infusion was delayed +1	Last non-zero dose date of agent – first dose date of the agent -total days infusion was delayed +1	Date of decision to discontinue or cut-off date – first dose date of agent – total days with dose received of 0 mg +1
Overall duration of study treatment (including holds)	(Maximum (date of last non-zero dose of nivolumab or ipilimumab or date of decision to discontinue cabozantinib/placebo or cut-off date) – date of first dose of study treatment + 1) / 30.4375		
Overall duration of study treatment (excluding holds)	Overall duration of study treatment (including holds) – total number of days dose was held, or infusion was delayed		

**Table 5: Study Therapy Definitions (Weight Based Cycles 1-4)**

	Nivolumab	Ipilimumab	Cabozantinib/Placebo
Intended dose for each cycle (i) for infusion components and in mgs for oral components	3 mg/kg/3wk for i=1-3; 3 mg/kg/4wk for i=4	1 mg/kg/3wk for i=1-4	40 mg once daily
Dose (i)	Total dose administered in mgs for each cycle is collected on the CRF	Total dose administered in mgs for each cycle is collected on the CRF	Total dose for the interval is collected on the CRF
Cycle duration (i) (wk)	(Dose date (i+1) - Dose date (i) )/7 for i=1-3 i=4, 28/7=4 wks	(Dose date (i+1) - Dose date (i) )/7 for i=1-3 i=4, 21/7=3 wks	NA
Cycle intensity (i) (mg/kg/wk)	Dose (i) /Cycle duration (i) i=1-4	Dose (i) /Cycle duration (i) i=1-4	NA
Relative cycle intensity (i) (%)	(Cycle intensity (i) / intended dose (i) ) × 100 for i=1-4	(Cycle intensity (i) / intended dose (i) ) × 100 for i=1-4	NA
Relative dose intensity (%)	Sum of all relative cycle intensities divided by number of weight-based infusions received	Sum of all relative cycle intensities divided by number of weight-based infusions received	See Table 4

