#### **6.6.3.1 Immune-related Adverse Events (irAEs)**

The immune-modulating properties of ICIs, such as the anti-PD-1 antibody nivolumab, and anti-CTLA-4 antibody ipilimumab are able to undermine immunologic tolerance and generate a subset of AEs (called immune related AEs or irAEs) with an autoimmune inflammatory pathomechanism. IrAEs may involve every organ or tissue (Michot et al 2016). Most irAEs occur within the first 12 weeks of exposure to ICIs but some of them may appear with a delayed onset. Diagnosis of irAEs should be based on exposure to an ICI and a reasonable immune-based mechanism of the observed AE. Whenever possible, histologic examination or other immune-based diagnostic evaluations should be used to support the diagnosis. Other etiologic causes including AEs from tumor progression should be ruled out.

The spectrum of irAEs is wide and can be general or organ-specific. Examples of general irAEs in subjects treated with ICIs such as nivolumab are fatigue, fever, and chills. Organ-specific irAEs consist of pneumonitis, colitis, hepatitis, nephritis and renal dysfunction, skin adverse reactions, encephalitis, myocarditis, and endocrinopathies (hypophysitis, adrenal insufficiency, hyperglycemia).

Early recognition and management of irAEs associated with immuno-oncology agents may mitigate severe toxicity. Medical management of irAEs focuses on suppressing the immune response with non-steroidal and steroid anti-inflammatory medication. Management algorithms have been developed and should be followed for subjects with suspected irAEs. Further information on management of nivolumab/ipilimumab-associated irAEs is provided in [Section 6.6.3.2](#) and [Appendix E](#), and can also be found in the US PI.

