**Table 6: Study Therapy Definitions (Flat Dose Cycles From 5 Onwards)**

	Nivolumab	Cabozantinib or Placebo
Dosing schedule per Protocol	480 mg every 4 weeks	40 mg once daily
Relative dose intensity (%)	Cumulative dose (mg)/[(Last non-zero dose date – First dose date of flat doses + 28) × 480/28)] × 100	See Table 4

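### The nivolumab relative dose intensity ignores a late infusion 5, because SAP Table 5 fixes cycle 4 at 28 days and Table 6 starts its clock at the first flat dose

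*SAP*

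**What the plan says.** SAP Section 6.5.3 reports three nivolumab RDIs: infusions 1-4, infusions 5 onwards, and overall. They are built in three tables.

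- **Table 5 (weight-based cycles).** The intended dose is "3 mg/kg/3wk for i=1-3; 3 mg/kg/4wk for i=4". Cycle duration is the actual interval to the next infusion for cycles 1 to 3, and a constant for cycle 4: "for i=1-3 i=4, 28/7=4 wks". The RDI for this part is "Sum of all relative cycle intensities divided by number of weight-based infusions received".
- **Table 6 (flat doses).** The time base is "Last non-zero dose date – First dose date of flat doses + 28" days, so it opens on the day of infusion 5.
- **Table 4 (overall).** The two parts are combined as "Relative dose intensity (%) during weight-based infusions × number of weight-based infusions received" plus "Relative dose intensity (%) of flat dose infusions × number of flat dose infusions received) / total infusions received". There is no other time term.

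The schedule in Protocol Appendix A puts infusion 4 at W10D1 and infusion 5 at W14D1, a planned gap of 4 weeks. Protocol Section 6.6.3 does not allow nivolumab dose reductions; AEs are handled by delay, or by discontinuation under Tables 6-3 and 6-10.

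**The concern.** For cycles 1 to 3, a late next infusion lengthens the cycle and lowers RDI. Table 5 also assigns the gap between infusions 4 and 5 to cycle 4, since its intended dose is expressed per 4 weeks. It then replaces the observed gap with the planned one, and Table 6 does not pick the gap up. A subject who received dose 4 in full scores 100% for that cycle however late infusion 5 was.

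At stake is the accuracy of a descriptive exposure statistic that will be shown by arm. The documents make delays at this point plausible. Protocol Section 6.6 lists raised liver tests as an overlapping toxicity. Protocol Table 6-3 delays nivolumab and ipilimumab, as well as interrupting the oral drug, for ALT or AST above 3 and up to 5 times ULN. Protocol Section 6.6.3.2.1 requires steroids to be tapered before nivolumab resumes.

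**Working it through.** **Inputs.** Cycle lengths, intended doses and formulas are from SAP Tables 4, 5 and 6; the planned dates are from Protocol Appendix A. Assumptions: full doses, no other delay, and a delay of d weeks before infusion 5. The range up to 12 weeks is illustrative. It borrows the limit in Protocol Section 6.6, beyond which interruption of all study treatment means discontinuation unless the Sponsor approves.

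**1. Reproduce the plan's figure.** 28/7 = 4 weeks, which equals the W10D1 to W14D1 gap. For a subject on schedule with four flat doses:
- each weight-based cycle is 100%;
- flat-dose RDI = 4 × 480 / [(84 + 28) × 480/28] = 1920/1920 = 100%;
- overall = (4 × 100 + 4 × 100)/8 = 100%.

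**2. Add the delay, formulas as written.** Cycle 4 remains 4/4 = 100%. The first and last flat-dose dates move together, so Table 6 is unchanged. All three RDIs remain 100% for any d.

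**3. Use the actual interval for cycle 4.**
- Cycle 4 = 100 × 4/(4 + d)
- Infusions 1-4 = (300 + cycle 4)/4
- Overall, four flat doses = (4 × RDI for infusions 1-4 + 4 × 100)/8

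| d (weeks) | Cycle 4 | Infusions 1-4 | Overall |
|---|---|---|---|
| 4 | 50.0% | 87.5% | 93.8% |
| 8 | 33.3% | 83.3% | 91.7% |
| 12 | 25.0% | 81.3% | 90.6% |

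**4. Move the same delay around.** Take one 6-week delay with four weight-based and six flat doses, using the SAP formulas as written:
- between infusions 3 and 4: cycle 3 = 3/9 = 33.3%; infusions 1-4 = 83.3%; overall = (4 × 83.3 + 6 × 100)/10 = 93.3%;
- between infusions 5 and 6: flat RDI = 6 × 28/(140 + 42 + 28) = 168/210 = 80%; overall = (4 × 100 + 6 × 80)/10 = 88.0%;
- between infusions 4 and 5: overall = 100.0%.

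With the actual cycle 4 interval, the last case becomes 4/10 = 40% for cycle 4, 85.0% for infusions 1-4 and (4 × 85 + 6 × 100)/10 = 94.0% overall. The overstatement is 15.0 points for infusions 1-4 and 6.0 points overall.

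**5. Dilution.** For the same 6-week delay and n flat doses, corrected overall RDI = (4 × 85 + 100n)/(4 + n). This is 88.0% for n = 1, 94.0% for n = 6 and 97.8% for n = 23. The infusions 1-4 figure does not depend on n.

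**The case against.** The best defence is that the convention is deliberate and the delay is visible elsewhere. Giving the last cycle of a phase its planned length matches ipilimumab cycle 4 and the 28 days added after the last flat dose, and it keeps the two dosing phases separate. Duration of exposure including delays (Table 4, Section 6.5.3) contains the interval. Delays due to AEs and exceeding 3 days appear by component in Section 6.6.2, with counts, durations and times to onset. Exposure is summarised descriptively, and no formal safety comparison between arms is planned.

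All of this stands as a limit on importance, but it does not make the RDI right. A planned length is needed only where no later infusion exists to close the cycle; ipilimumab has no fifth dose, but nivolumab continues. Duration including delays cannot distinguish a delay from longer treatment, and Section 6.6 restricts modification summaries to AE causes.

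Four stronger readings are tempting and are not supported:

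- **That the delay is recorded nowhere and loss of exposure is hidden.** It is absent from dose intensity only.
- **That RDI is biased in favour of the triplet arm.** Neither document gives a frequency of delays at this point, so no arm-level effect can be computed. Nor does the SAP designate RDI as its measure of whether cabozantinib reduces nivolumab delivery.
- **That this is among the likeliest delays.** Protocol Section 6.6.3.1 says "Most irAEs occur within the first 12 weeks of exposure to ICIs". Infusions 2, 3 and 4 (W4, W7, W10) fall inside that window and their lateness is counted; infusion 5 is due at W14. Some toxicities also lead to discontinuation, after which there is no infusion 5.
- **That the overstatement should be read on elapsed time.** With four flat doses and a 12-week delay that would be 29/(29 + 12) = 70.7%, but the SAP does not use this metric and the fix does not recover it. A 12-week delay in cycle 3, counted as the SAP intends, gives cycle 3 = 3/15 = 20%, infusions 1-4 = 80%, and overall (4 × 80 + 4 × 100)/8 = 90%. Most of the gap to 70.7% comes from averaging cycle ratios by infusion count.

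**Conclusion.** The point holds for nivolumab dose intensity and no further. As written, no delay between infusions 4 and 5 lowers any of the three RDIs, so the infusions 1-4 and overall figures are overstated for every subject whose infusion 5 is late. Under the assumptions above, delays of 4 to 12 weeks overstate the infusions 1-4 RDI by 12.5 to 18.8 points, and the overall RDI with four flat doses by 6.3 to 9.4 points. The overall effect is smaller with more flat doses. Subjects whose infusion 5 was on time, or who stopped after infusion 4, are unaffected. A difference in bias between arms is possible but not shown. No efficacy test, alpha or power figure depends on this. It is worth correcting because the rule treats equal delays unequally according to where they fall, and the remedy is already in the SAP's own rule for cycles 1 to 3.

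**What to change.** In SAP Table 5, nivolumab column, cycle duration for i = 4: use (Dose date(5) − Dose date(4))/7 when infusion 5 was given, and 4 weeks only when infusion 4 was the last nivolumab infusion. Keep the per-4-week intended dose as the reference for cycle 4. Leave ipilimumab, Table 6 and the Table 4 weighting unchanged.

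The cost is one line of SAP wording and one line of code. Reported nivolumab RDI becomes somewhat less favourable where infusion 5 was late. SAP Section 4.8 allows minor corrections that do not materially change an analysis to be documented in an addendum, which would suit this one.

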**Table 6: Study Therapy Definitions (Flat Dose Cycles From 5 Onwards)**

	Nivolumab	Cabozantinib or Placebo
Dosing schedule per Protocol	480 mg every 4 weeks	40 mg once daily
Relative dose intensity (%)	Cumulative dose (mg)/[(Last non-zero dose date – First dose date of flat doses + 28) × 480/28)] × 100	See Table 4

### 6.5.1. Overall Exposure

Overall study treatment exposure will be summarized as follows:

- Descriptive summary for duration of exposure (including dose holds) of study treatment in months calculated as [maximum of (date of last non-zero dose of nivolumab or ipilimumab or date of decision to discontinue cabozantinib/placebo or cutoff date – date of first dose of study treatment+1)/30.4375]. Categorical summary presented in months:  $\leq 3, > 3, > 6, > 12, > 24$

- Descriptive summary for duration of exposure (excluding dose holds) of study treatment in months calculated as duration of exposure (including dose holds) – total number of days dose was held or infusions were delayed
- Descriptive summary for duration of exposure (including dose holds) of the first study treatment component discontinued in months calculated as [minimum of (date of last non-zero dose of nivolumab or ipilimumab or date of decision to discontinue cabozantinib/placebo or cutoff date – date of first dose of study treatment+1)/30.4375]. Categorical summary presented in months:  $\leq 3, > 3, > 6, > 12, > 24$
- Descriptive summary for duration of exposure (including dose holds) of the first component discontinued for treatment combination cabozantinib/placebo+nivolumab in months calculated as [minimum of (date of last non-zero dose of nivolumab or date of decision to discontinue cabozantinib/placebo or cutoff date – date of first dose of cabozantinib/placebo+nivolumab treatment+1)/30.4375]. Categorical summary presented in months:  $\leq 3, > 3, > 6, > 12, > 24$

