### **6.5.2. Exposure for Cabozantinib/Placebo Component**

Exposure for cabozantinib/placebo treatment will be summarized as follows:

- Duration of exposure (including dose holds) calculated as (earlier of date of decision to discontinue oral component or cutoff date – date of first dose of oral component + 1) /30.4375
- Duration of exposure (excluding dose holds) calculated as (earlier of date of decision to discontinue oral component or cutoff date – date of first dose of oral component - total days with oral dose received of 0 mg + 1) /30.4375
- Average daily dose (mg/day) calculated as (total mg received/duration of exposure in days)
- Percent dose intensity, calculated as  $100 \times (\text{average dose in mg/day})/(40 \text{ mg/day})$

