### 6.6.2. Dose Holds (Delays) due to Adverse Events

Nivolumab or ipilimumab infusion may be delayed. An infusion was considered delayed if the delay exceeded by 3 days for nivolumab/ipilimumab. For cabozantinib/placebo dose was considered as held if the subject did not take the dose of the medication. The following hold/delay summaries due to AE for study treatment, both infusion components due to the same AE and each treatment component will be presented:

- Subjects with any dose delay/hold
- Frequency counts and percentages for subjects with any dose hold, hold  $\geq$  7 days,  $\geq$  14 days,  $\geq$  21 days
- Descriptive statistics for number of dose holds (0 mg dose level) due to an AE per subject and classified as 1, 2, 3, and  $>3$
- Descriptive statistics for total duration of dose holds per subject due to an AE, where duration of each dose hold is calculated as (stop date of hold – start date of hold + 1). Categorical summaries for  $\geq$  7 days,  $\geq$  14 days, and  $\geq$  21 days will also be presented
- Descriptive statistics for duration of each dose holds due to an AE, calculated as (stop date of hold – start date of hold + 1). Categorical summaries for  $\geq$  7 days,  $\geq$  14 days, and  $\geq$  21 days will also be presented
- Descriptive statistics for time to first dose hold (also presented for study treatment), time to first dose hold that was  $\geq$  7 days,  $\geq$  14 days, and  $\geq$  21 days. The time to dose hold is calculated as (start date of the hold – first dose date + 1)
- Descriptive statistics for time to second dose hold, time to second dose hold that was  $\geq$  7 days,  $\geq$  14 days, and  $\geq$  21 days

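### SAP overall exposure excluding holds subtracts days from months, and Table 5 relative dose intensity lacks a body-weight term and a duration for the last infusion of subjects who stop early

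*SAP*

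**What the plan says.** **Overall exposure.** SAP Section 6.5.1 and Table 4 express overall duration including holds in months, dividing by 30.4375. For the version excluding holds, Section 6.5.1 gives a duration "in months calculated as duration of exposure (including dose holds) – total number of days dose was held or infusions were delayed", and Table 4 gives "Overall duration of study treatment (including holds) – total number of days dose was held, or infusion was delayed". Neither converts the days. For the oral component alone, Section 6.5.2 takes the zero-dose days off inside the bracket and divides afterwards: "total days with oral dose received of 0 mg + 1) /30.4375". An infusion delay has its own definition, separate from an oral hold (Section 6.6.2: "An infusion was considered delayed if the delay exceeded by 3 days for nivolumab/ipilimumab").

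**Weight-based relative dose intensity.** In Table 5 the nivolumab and ipilimumab dose for cycle i is described as "Total dose administered in mgs for each cycle is collected on the CRF". Cycle intensity is that dose over the cycle duration in weeks, labelled mg/kg/wk. It is then compared with an intended dose per kilogram, for nivolumab "3 mg/kg/3wk for i=1-3; 3 mg/kg/4wk for i=4".

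**Cycle duration.** For cycles 1 to 3 it is the gap to the next dose date. A fixed value exists only for cycle 4: four weeks for nivolumab, three for ipilimumab. The sum of relative cycle intensities is divided by all weight-based infusions received. Table 4 divides the ipilimumab sum by an N that it does not define.

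**The concern.** Three formulas cannot give the quantity they name if programmed as printed.

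- The overall duration excluding holds mixes units.
- The weight-based dose intensity has milligrams above and milligrams per kilogram below.
- A subject whose last infusion is the first, second or third has no duration for that cycle, yet the infusion counts in the divisor. Such subjects are expected: Section 6.5.4 tabulates early ipilimumab discontinuation by one, two or three doses.

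At stake is the description of treatment delivery by arm. In an add-on trial, the dose intensity of the nivolumab and ipilimumab backbone shows whether the third agent reduced its delivery. If early stopping differs between arms, an artefact tied to early stopping can appear as a difference in dose intensity.

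**Working it through.** The documents state no numerical result for these formulas, so there is no figure to reproduce. The check evaluates them as printed and then with consistent units. The month of 30.4375 days is from SAP Section 4; the example durations, weights and infusion counts are assumptions.

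**1. Months minus days.** Let E be exposure days and h held or delayed days.

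- As printed: E/30.4375 - h. With E = 365.25 and h = 30: 12 - 30 = -18.
- Days first, as in Section 6.5.2: (E - h)/30.4375 = 335.25/30.4375 = 11.01.
- The printed value is negative when h > E/30.4375, that is when h/E > 1/30.4375 = 3.29%. At 12 months, 13 held days already give 12 - 13 = -1; the consistent value is 352.25/30.4375 = 11.57.
- Correcting the units leaves one question open. If oral and infusion treatment are both off for the same 30 days and both are counted, the result is (365.25 - 60)/30.4375 = 10.03 instead of 11.01.

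Table 4's component rows for duration are in days throughout and do not have this fault.

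**2. No weight term.** Take 80 kg, full dose, on schedule.

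- Nivolumab cycles 1 to 3: 240 mg / 3 wk = 80, against 3/3 = 1 mg/kg/wk, giving 8000%.
- Nivolumab cycle 4: 240 / 4 = 60, against 3/4 = 0.75, giving 8000%.
- Ipilimumab: 80 / 3 = 26.7, against 1/3 = 0.333, giving 8000%.

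The printed value is weight in kg × 100%, so 5000% at 50 kg and 11000% at 110 kg. Dividing the dose by weight returns 100% in every case.

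Table 4's ipilimumab value inherits the whole factor. Its overall nivolumab value averages weight-based and flat infusions, and the flat ones (Table 6) carry no weight error. With 4 weight-based and 10 flat infusions at 80 kg: (8000 × 4 + 100 × 10)/14 = 2357%.

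The choice of weight also matters. Protocol Section 6.2 requires a dose adjustment only when weight changes by at least 10% from baseline. For a subject still correctly dosed on baseline weight, dividing by visit weight gives 100/0.91 = 109.9% after a 9% loss and 100/1.09 = 91.7% after a 9% gain.

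**3. No duration for an early last infusion.** Assume the weight term is corrected, dosing is on schedule, n infusions are received (n < 4), and the undefined term is left out of the sum. The result is (n - 1) × 100/n:

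| Infusions received | Term left out | Planned 3 weeks used |
|---|---|---|
| 1 | 0% | 100% |
| 2 | 50% | 100% |
| 3 | 66.7% | 100% |

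Under the same handling, if a share p of an arm stops on schedule after two infusions and everyone else scores 100%, the arm mean is 100 - 50p, so p = 0.10 gives 95%.

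**The case against.** The strongest reply is that the intention is visible in each case. Section 6.5.2 shows the right order of operations, the printed unit mg/kg/wk shows that division by weight was meant, and the last-dose convention appears in Table 5 for cycle 4 and in Table 6, which adds 28 days after the last flat dose. Negative months and 8000% would be noticed. The outputs are descriptive, SAP Section 8 plans no formal safety comparison between arms, and Section 6.5.4 reports infusions received and early discontinuation separately.

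This stands as an argument about severity. It does not supply the missing choices: which weight, how overlapping holds count, and what interval applies to an early last infusion.

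Four stronger readings are tempting, and the documents do not support them:

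- A reader might infer that Table 4's overall nivolumab intensity is inflated by the full body weight. Flat doses dilute the error, hence 2357% rather than 8000% in the example.
- A reader might infer that the early-stopping error would pass unseen. The 0%, 50% and 66.7% values follow from one way of handling an undefined term, which the SAP does not prescribe, and 0% for a subject who was dosed would be conspicuous.
- Section 6.5.1 lists the cutoff date inside a maximum ("maximum of (date of last non-zero dose of nivolumab or ipilimumab or date of decision to discontinue cabozantinib/placebo or cutoff date"), and a reader might infer that subjects who stopped treatment are credited up to the cutoff. The natural reading is that the cutoff applies when oral treatment is ongoing, as Section 6.5.2 says ("earlier of date of decision to discontinue oral component or cutoff date"). The wording should be aligned, but it is not a separate error.
- A reader might take counting overlapping days once as the only correct rule. It depends on whether excluding holds means that any component was held or that all were, and the SAP does not say.

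**Conclusion.** The three defects are present in the current SAP text and the formulas are wrong as written. Overall exposure excluding holds turns negative above 3.29% held days. Weight-based relative dose intensity is too large by a factor equal to body weight in kg, carried fully into Table 4's ipilimumab value and partly into its overall nivolumab value. The early-stopper gap gives 0%, 50% or 66.7% only if the undefined term is dropped while the divisor is kept. Any distortion between arms also requires early stopping to differ between them, which the documents do not establish.

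Severity is minor. Only descriptive exposure summaries in the Safety and P-Safety populations are affected; PFS, OS, power and type I error are not.

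**What to change.** Issue an addendum to the SAP, which Section 4.8 allows for clarifications and minor corrections:

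- **Section 6.5.1 and Table 4, overall duration:** subtract held or delayed days before dividing by 30.4375. State whether a day counts when any component or only when every component is off, and how overlapping oral holds and infusion delays are counted.
- **Cutoff:** use the earlier of the oral decision date and the cutoff, as in Section 6.5.2, before taking the latest date across components.
- **Table 5, weight:** divide each dose by the weight on which that infusion's dose was based, and name the source variable.
- **Table 5, last infusion:** use the planned interval for the last infusion a subject received, as Table 5 does for cycle 4 and Table 6 for flat doses.
- **Table 4:** define N as infusions received.

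The cost is the addendum and a change to the programming specification. Doses and dose dates are already used in Table 5, and post-baseline weight is summarised in SAP Section 8.8. The documents do not show that the dosing weight itself is recorded. If it is not, the addendum must state a fallback. Using baseline weight unless the 10% rule applied would give 91% for a fully dosed subject whose site dosed on current weight after a 9% loss (0.91 × 100), so that limitation should be footnoted.
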